#### 1.2 Secondary Objectives

- A. To evaluate the ability of **locally administered** TLR agonist (R848 gel) to activate innate immune cells at the gp100 (g209-2M) **vaccine site**.
- B. To evaluate the ability of R848 gel, administered at the **tumor site**, to:
  - i. Induce inflammation and upregulation of adhesion molecules on tumor vasculature
  - ii. Enhance T-cell infiltration into tumor
  - iii. Generate T-cells against additional tumor antigens, not present in the vaccine (i.e., antigen spreading).
  - iv. Mediate clinical response with measure of objective tumor response rate and progression free survival.

C. To assess the association between clinical response and laboratory parameters of T-cell priming, T-cell migration to tumor, and inflammation at the vaccine and tumor sites.

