**9.2 Definition of Index/Non-Index Lesions**

In many patients, all measurable disease will be cutaneous, so we will allow all 10 index lesions to be in a single organ. All measurable lesions, up to a maximum of ten lesions in total, should be identified as *index* lesions to be measured and recorded on the medical record at baseline. The *index* lesions should be representative of all involved organs. In addition, *index* lesions should be selected based on their size (lesions with the longest diameters), their suitability for accurate repeat assessment by imaging techniques, and how representative they are of the patient's tumor burden. A sum of the products of diameters (SPD) for all *index* lesions will be calculated and considered the baseline sum of the products of diameters. Response criteria to be followed are listed below. The baseline sum will be used as the reference point to determine the objective tumor response of the *index* lesions at tumor assessment (TA). Measurable lesions, other than *index* and all sites of non-measurable disease will be identified as *non-index* lesions. *Non-index* lesions will be recorded on the medical record and should be evaluated at the same assessment time points as the *index* lesions. In subsequent assessments, *non-index* lesions will be recorded as "stable or decreased disease," "absent", or "progression."

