**Definition of Index Lesions Response Using irRC**

**irComplete Response (irCR):** Complete disappearance of all *index* lesions. This category encompasses exactly the same subjects as "CR" by the mWHO criteria.

**irPartial Response (irPR):** Decrease, relative to baseline, of 50% or greater in the sum of the products of the two largest perpendicular diameters of all *index* and all new measurable lesions (i.e., Percentage Change in Tumor Burden). Note: the appearance of new measurable lesions is factored into the overall

tumor burden, but does not automatically qualify as progressive disease until the SPD increases by  $\geq 25\%$  when compared to SPD at nadir.

**irStable Disease (irSD):** Does not meet criteria for irCR or irPR, in the absence of progressive disease.

**irProgressive Disease (irPD):** At least 25% increase Percentage Change in Tumor Burden (i.e., taking sum of the products of all *index* lesions and any new lesions) when compared to SPD at nadir.

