#### **Definition of Non-Index Lesions Response Using irRC**

**irComplete Response (irCR):** Complete disappearance of all *non-index* lesions. This category encompasses exactly the same subjects as "CR" by the mWHO criteria

**irPartial Response (irPR) or irStable Disease (irSD):** *non-index* lesions are not considered in the definition of PR, these terms do not apply.

**irProgressive Disease (irPD):** Increases in number or size of *non-index* lesions does not constitute progressive disease unless/until the Percentage Change in Tumor Burden increases by 25% (i.e., the SPD at nadir of the index lesions increases by the required amount).

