#### **9.4 Definition of Overall Response Using irRC**

Overall response using irRC will be based on these criteria:

**Immune-Related Complete Response (irCR):** Complete disappearance of all tumor lesions (index and non-index together with no new measurable/unmeasurable lesions) for at least 4 weeks from the date of documentation of complete response.

**Immune-Related Partial Response (irPR):** The sum of the products of the two largest perpendicular diameters of all index lesions is measured and captured as the SPD baseline. At each subsequent tumor assessment, the sum of the products of the two largest perpendicular diameters of all index lesions and of new measurable lesions are added together to provide the Immune Response Sum of Product Diameters (irSPD). A decrease, relative to baseline of the irSPD compared to the previous SPD baseline, of 50% or greater is considered an immune Partial Response (irPR).

**Immune-Related Stable Disease (irSD):** irSD is defined as the failure to meet criteria for immune complete response or immune partial response, in the absence of progressive disease.

**Immune-Related Progressive Disease (irPD):** It is recommended in difficult cases to confirm PD by serial imaging. Any of the following will constitute progressive disease:

- At least 25% increase in the sum of the products of all index lesions over baseline SPD calculated for the index lesions.
- At least a 25% increase in the sum of the products of all index lesions and new measurable lesions (irSPD) over the baseline SPD calculated for the index lesions.

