#### **9.6 Baseline measurement**

In this trial a period of immunization opens the treatment, and immunization alone mediates tumor response rarely. (Cancer immunotherapy: moving beyond current vaccines. Rosenberg SA, Yang JC, Restifo NP. *Nat Med.* 2004 Sep;10(9):909-15.) So with this sequence, as has been seen with other immunologic mediators, we should expect that a period of progression may precede any response from the treatment.

Therefore, because subjects are likely to progress during the vaccination portion of the study, the baseline will be that measurement during the first 10 weeks of the study at which the tumors are at their maximum size (based on sum of LD). Progression will be allowed during these first 10 weeks without withdrawal of the subject from treatment or from the study. This includes increase in the size of the lesions as well as the appearance of new lesions.

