### **Additional Cohort of Non-Randomized Patients**

As noted above in the Overview, after the initial 48 patients have been enrolled in the randomized portion of the trial, 20 additional patients with metastatic disease will be enrolled into Arm C in order to further characterize tumor response of R848. These patients will not be included in the primary analysis. Tumor response as measured by a 50% shrinkage in tumor size by irRC criteria will be the primary endpoint for these patients. The response rate associated with the standard of care in these patients is no more than 5%. We expect a total of 10 metastatic disease patients in Arm A from the initial randomized portion of the trial. Combined with the additional 20 patients (Arm A and C, with a total of 30 patients, we will have 82% power to detect an increase to 22%, assuming a one-sided exact binomial test with a 5% Type I error rate.

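### Section 9.6 picks the response baseline on sum of LD although response is scored on SPD, and irPD is measured from nadir in 9.3 but from baseline in 9.4

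*Combined protocol and SAP*

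**What the plan says.** **Choice of baseline.** Section 9.6 explains that growth during vaccination is expected, and therefore takes as baseline the measurement in "the first 10 weeks of the study at which the tumors are at their maximum size (based on sum of LD". LD is not spelled out; I read it as longest diameter.

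**Measure used for scoring.** Section 9.2 works on another scale: the SPD of all index lesions "will be calculated and considered the baseline sum of the products of diameters". Section 9.4 defines irPR on that scale: "A decrease, relative to baseline of the irSPD compared to the previous SPD baseline, of 50% or greater".

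**Progression.** Under section 9.3, index-lesion irPD is a rise of at least 25% in the burden of index lesions "and any new lesions) when compared to SPD at nadir". The non-index paragraph of 9.3 uses the same reference: "the SPD at nadir of the index lesions increases by the required amount". Section 9.4, on overall response, instead lists "At least 25% increase in the sum of the products of all index lesions over baseline SPD calculated for the index lesions", and its second criterion, which adds new measurable lesions, also refers to baseline. The table of irRC definitions that follows 9.4 gives +25% with no reference point.

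**Where these rules are used.** A 50% shrinkage by irRC is the primary endpoint for Arm C and for the pooled Arm A and C test (section 11.0, Additional Cohort of Non-Randomized Patients). Section 1.2 lists as a secondary objective "Mediate clinical response with measure of objective tumor response rate and progression free survival".

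**The concern.** A response rule needs one measure throughout. Here the baseline visit is chosen on a one-dimensional sum, and the percentage change is then taken on a two-dimensional one. The stated aim of 9.6 is to count from the largest tumour burden. On the scale that decides response, the LD rule can miss that reading.

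The progression conflict is separate and wider. After any shrinkage, nadir lies below baseline, so 9.3 and 9.4 call irPD at different tumour burdens. Two analysts who each follow the protocol could class the same patient differently. This reaches any endpoint built on progression, and the passages on handling progression that rely on irPD.

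**Working it through.** **1. The plan's own figure.** Inputs from section 11.0: n = 30, null rate 5%, alternative 22%, one-sided exact binomial test at 5%.

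- P(X ≥ 4 | 30, 0.05) = 0.0608, which is too large.
- P(X ≥ 5 | 30, 0.05) = 0.0156, so the cut is 5 or more responses.
- P(X ≥ 5 | 30, 0.22) = 0.821.

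The stated 82% reproduces. The same cut exceeds 5% error only if the true null rate passes 6.8%, where P(X ≥ 5 | 30, 0.068) = 0.05.

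**2. LD against SPD.** The lesion sizes below are chosen for illustration.

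| Reading | Lesions (mm) | Sum of LD | SPD |
|---|---|---|---|
| A | 22×12, 18×10 | 22 + 18 = 40 | 264 + 180 = 444 |
| B | 21×15, 18×12 | 21 + 18 = 39 | 315 + 216 = 531 |
| Later | 15×10, 12×9 | not needed | 150 + 108 = 258 |

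Section 9.6 picks A, because 40 > 39. The later change is 258/444 − 1 = −42% from A, which is irSD. From B it is 258/531 − 1 = −51%, which is irPR if confirmed.

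In general, if the LD rule picks a reading other than the one with the largest SPD, the picked SPD cannot be the larger. Any later SPD between half of the picked value and half of the maximum loses its response. Here that range is above 222 and up to 265.5.

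**3. How often this matters.** The documents give no lesion-level variances, so a simulation has to assume them. It used readings at weeks 0 and 8 only, two or five lesions per patient, and no new lesions. The LD rule picked the smaller SPD in about 3–10% of patients. It changed the response class in only 0.03–0.2% of patients when the response rate was 3–5%, and in 0.1–0.5% when it was 22%. At the top of that range, 0.005 × 30 = 0.15 patients in the pooled test.

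**4. Nadir against baseline.** Let n be nadir SPD divided by baseline SPD. Section 9.3 calls irPD at 1.25 × n of baseline; section 9.4 calls it at 1.25 of baseline. For any n below 1, the burdens in between are classed differently.

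- Baseline 100, nadir 40, current 55: 55/40 − 1 = +37.5%, irPD under 9.3; 55/100 − 1 = −45%, irSD under 9.4.
- Nadir at 50% of baseline: irPD at 62.5% of baseline under 9.3 and at 125% under 9.4.

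**5. Which reading can be the nadir.** Suppose SPD is 70 at week 0, 100 at week 8 (taken as baseline) and 95 at week 16. That is 95/100 − 1 = −5% from baseline, but 95/70 − 1 = +36% if the week-0 value may serve as nadir. Section 9.3 does not say.

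**The case against.** **The LD slip is trivial.** It is a one-word error with almost no effect on the response rate. That is right as to size, and the 82% power is untouched. It remains a wrong measure in the definition of a primary endpoint, and it costs one word to correct.

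**Section 9.4 governs.** One can argue that 9.3 only defines the index and non-index components, and that 9.4 decides overall response, so there is no conflict. This does not hold, because the table after 9.4 feeds the index-lesion category into overall response. A patient with index-lesion irPD from nadir whose burden is 45% below baseline fits no row of that table if change is counted from baseline. The table names no reference that would settle it.

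**Week 0 as nadir is strained.** Section 9.6 exists to set aside growth in the first 10 weeks, so nadir is probably meant to run from the chosen baseline onward. I accept that as the likely intent, but the text does not say so.

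**A stronger reading: inflated Type I error.** A reader might infer that a maximum-size baseline makes the 30-patient test anti-conservative. On one and the same measure, a maximum can indeed only hold or raise the response rate relative to a fixed reading. But the reset is a stated and reasoned choice, and the comparator is given as a bound: "The response rate associated with the standard of care in these patients is no more than 5" per cent, with no baseline named. The cut tolerates a null rate up to 6.8%. The documents give neither the growth nor the variances needed to tell whether that is passed, so the inference is not established.

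**A second stronger reading: two definitions of progression-free survival.** It is named in section 1.2, but section 11.0 neither defines nor analyses it. What is defined twice is irPD.

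**Conclusion.** The plan is wrong as written on two endpoint rules.

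- **Baseline measure.** Choosing the baseline on LD and scoring on SPD can cost a patient a response. On assumed variances this happens in at most about 0.5% of patients, so the effect on the response rate is small. The contradiction itself rests only on the text and on reading LD as longest diameter.
- **irPD reference.** The conflict between 9.3 and 9.4 needs no assumptions. It leaves the class undetermined for any patient who shrinks and then regrows to a burden between the two thresholds. How many patients that would be cannot be found from the documents.

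Neither point disputes the sample size or the power of the pooled test.

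**What to change.** 1. In section 9.6, replace sum of LD with SPD, computed as in 9.2.
2. Reconcile the irPD reference across 9.3, 9.4 and the table of irRC definitions, and the passages on progression that depend on it. State whether nadir is counted from the 9.6 baseline onward. I take no view on which reference is right.
3. Add a sensitivity analysis of response from the fixed week-8 SPD. Section 6.0 already has the target tumours measured at the end of the eight vaccine weeks, and section 11.0 has clinical response assessed at week 8, so no new data are needed.
4. Date the change and show the result under the LD rule beside the corrected one. Section 11.0 (Part 1) records that more than 24 patients had reached week 24 by September 2013, so the correction cannot be presented as set in advance for everyone.

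The cost is an amendment to wording and one extra analysis. The downside is that the response rate may look slightly less favourable from the fixed week-8 reading.

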### **10.0 Criteria for Removal From The Study**

#### **10.1 Disease progression:**

All patients who develop recurrent disease will be taken off the study. Patients in the either cohort may complete their laboratory evaluation (blood draws, biopsies and pharesis) if they recur/progress before week 16. Patients will be allowed to continue on the study if their disease progresses during the first 10 weeks of study, since they will have only received vaccine +/- local TLR agonist at this point. For subsequent evaluations, patients with progressive disease will be removed from the treatment.

#### **10.2 Withdrawal of consent:**

The patient's desire to withdraw from the study may occur at any time. If a patient withdraws consent, the investigator will assess whether the reason for withdrawal is actually an adverse event, in which case the adverse event should be noted as the reason for withdrawal.

#### **10.3 Adverse event:**

Including unacceptable toxicity or exacerbation of underlying disease associated with treatment and necessitating discontinuation of treatment, usually associated with events that pose a threat to the patient's life or functioning. For example, any grade III or greater toxicity, attributable to the peptide vaccines or R848 (Resiquimod)

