infiltration, we plan to utilize this dose of R848 two times per week every 3-4 days (+/- 2 days), with the option of dose reducing from twice to once a week should patients experience any grade 3 or greater toxicity.

The physician will designate which of the two regions to receive or not to receive R848. (For example, if the cutaneous disease is limited to the thigh, the area of lesions will be divided in two with one region proximal and one region distal. Then the proximal region is assigned region A and the distal assigned region B. Resiquimod to be applied to region A or B. A 5mm margin will be included in the treatment area around each of the lesions at a spread rate of 10mcg/cm^2. The sum of the area of all treated lesions will not exceed 100cm^2. The treatment area will be allowed to air dry for 30 minutes and then covered with a gauze dressing which can be removed the following day. The R848 gel will be applied in the clinic by the research nurse for the first two weeks of administration, and then the subject will apply the gel at home thereafter. The patient will be trained for gel self-administration by the research staff. Sachets of gel will be supplied for home use and the subject will be instructed on maintaining a home record of administration. This home record or a progress note by one of the research team reviewing home administration may each act as a source document for all matters regarding home administration during this period. The gel may be applied in the clinic for longer than the first two weeks at the discretion of the investigators.

Tumor biopsies of treated and untreated lesions will be obtained as outlined in section 7.3 when feasible in order to assess T-cell infiltration and function at the site.

In order to give patients the opportunity to receive R848 gel on all their lesions, we will allow cross-over of patients who do not respond in untreated lesions by week 16 (8weeks after initiating gel on the tumors) in the untreated lesions to receive R848 gel on all of the lesions, but these patients will not be included in the final analysis of clinical endpoints that occur following week 24. Patients will not cross-over until after all blood, biopsies, and data are recovered for assessment of the primary endpoints in any subject. Treatment with R848 gel will continue for up to 4 months beyond week 24 as long as there is no disease progression.

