### 8.0 Serious Adverse Event Reporting (SAE)

Vaccines are usually well-tolerated. They may cause discomfort, swelling, and/or redness around the injection site. While there has not been significant autoimmune symptoms caused by gp100(g209-2M) or MAGE-3 peptide vaccines alone, patients who experience any Grade III or greater autoimmune reactivity, except for local skin reactions, will be taken off the study. The occurrence of 3 patients with Grade III or greater toxicity will stop the entry of the study until an assessment of the risks, coordination with MD Anderson IRB and appropriate modifications of the informed consent can be completed.

The most frequent systemic toxicities associated with Resiquimod are fever, fatigue, headache, pain, dizziness, myalgia, chills, and a small increase in absolute lymphocyte count. Localized toxicities reported are erythema, edema, ulceration, weeping, scabbing, flaking, pruritis, and numbness/tingling. Other infrequent toxicities reported that may be related are abnormal LFT, abdominal cramping, nausea, vomiting, diarrhea, backache, neck pain, rhinitis, and urticaria.

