**All adverse events will be recorded according to this table:**

Attribution	Grade 1	Grade 2	Grade 3	Grade 4	Grade 5
Unrelated			X	X	X
Unlikely			X	X	X
Possible	X	X	X	X	X
Probable	X	X	X	X	X
Definitive	X	X	X	X	X

Exceptions to this rule will include events and laboratory abnormalities that represent common symptoms and abnormalities of melanoma and chemotherapy and/or have no clinical significance:

- Abnormalities in hematologic parameters due to myelosuppressive therapeutic effect:
  - i. Anemia, neutropenia, lymphopenia, thrombocytopenia
  - ii. Epistaxis or bleeding except for catastrophic CNS or pulmonary hemorrhage
- Common symptoms of cancer (unless grade  $\geq 3$ ) including:
  - i. Fatigue
  - ii. Weakness
  - iii. Bone, joint or muscle pain
  - iv. Alopecia
  - v. Loss of appetite, Nausea, Vomiting
  - vi. Chemistry abnormalities (phosphorus, calcium, glucose)
  - vii. Coagulation abnormalities (shortened PT, PTT, increased fibrinogen)
- Laboratory abnormalities:
  - i. LDH (increased or decreased)
  - ii. Alkaline phosphatase (increased or decreased)
  - iii. Low levels of the following: AST, ALT, creatinine, BUN, uric acid, bilirubin, albumin, total protein
  - iv. Electrolyte abnormalities (sodium, potassium, bicarbonate, CO2, magnesium)

Abnormal laboratory test results will be captured if intervention is required.

Based on the CTCAE v.4, any grade 3 or greater toxicity will result in a dose reduction of the application of R848 from twice a week to once a week, however we will still report this AE. In addition, if this is required in 3 patients, we will temporarily halt accrual so that we can reassess the study as indicated. Abnormal lab values that are considered clinically significant by the principal investigator will be tracked. The criteria used is based on our experience with this assay in patients, was that biologically significant response is considered to be  $\geq 0.1\%$  gp100(g209-2M) tetramer + cells in the CD8 + T-cell population, and an increase of  $\geq 2$  fold of gp100(g209-2M) tetramer + cells at any time point over the pre-vaccine levels. This is based on the sensitivity of detection using our current tetramers and immunologic reagents.

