## 11.0 Statistical Considerations

### Overview

This is a randomized phase II trial enrolling melanoma patients who are HLA-A2+ with or without HLA-DP4+. Patients of two separate types will be enrolled in separate cohorts. One cohort includes patients who are NED but at high risk for recurrence. The second cohort will include patients with non-visceral metastatic disease and must have at least two evaluable and biopsiable lesions to be eligible for the trial.

The trial will have two parts. In Part 1 (both cohorts), we will fairly randomize patients to receive either the gp100(g209-2M) +/-MAGE3 peptide vaccine plus a topical TLR 7 /8 agonist, R848, (Arm A) or the gp100(g209-2M) +/- MAGE3 vaccine alone Arm B). The randomization will be stratified by cohort. A total of 48 patients will be enrolled, 24 per arm. All patients will receive the gp100(g209-2M) vaccine (those who are HLA-DP4 + will also receive the MAGE3 vaccine) weekly (for 8 weeks) and the patients randomized to receive R848 gel will have the gel applied to the gp100(g209-2M) vaccine site weekly.

After 8 weeks of treatment on Part 1, Part 2 of the trial begins. In Part 2 (only patients in the metastatic disease cohort), the treating physician will divide the area of cutaneous lesions into regions, Region A and Region B and designate the two regions to receive or not to receive R848. At least one lesion will be randomly assigned to receive R848 from weeks 8 through 24, and one will not. One lesion from each region will be chosen for biopsy as outlined in section 7.3. If a patient has more than two evaluable lesions, we will stratify by lesion size to assure that the lesions will be comparable.

As a safety measure, if a patient's untreated lesions grow while treated lesions are stable or shrink, all lesions will be treated with R848. This will occur after the assessment of the primary endpoints of the study, so it will not affect the analysis of these endpoints.

In April 2015, the trial is being further modified to add an additional 20 patients with metastatic disease, all of whom will receive the the gp100(g209-2M) +/-MAGE3 peptide vaccine plus R848 (Arm C). These patients will not be part of the primary comparative study analysis of T-cell responses in the blood. The purpose of these patients is to provide additional information on characterizing tumor response, defined as at least a 50% shrinkage in tumor size by irRC criteria.

### Part 1

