The primary objective of Part 1 of the trial is to compare T-cell responses in the blood between the vaccine+R848 and vaccine alone treatment arms. This will be assessed in the two cohorts separately and combined. The primary outcome of this part of the trial will be T-cell response to gp100(g209-2M) +/- MAGE3 measured at 8 weeks using a tetramer/multimer assay measured by flow cytometry. Based on the number of gp100(g209-2M) +/- MAGE3 T-cells measured, when the study began, patients were to be categorized as either immune responders or immune non-responders. From previous vaccine studies, a  $\geq 0.1\%$  response was thought to be a reasonable target. Thus, T-cell response to the gp100(g209-2M) + / - MAGE3 peptide in each patient was

defined as  $\geq 0.1\%$  gp100(g209-2M) tetramer+ cells in the CD8+ T-cell population or  $\geq 0.1\%$  MAGE3 multimer cells in the CD4+ T-cell population. In September 2013, due to problems in obtaining the multimers necessary to perform the CD4+ T-cell assays, these assays have not yet been run, although more than 24 patients have reached week 24 on the trial. Based upon the aggregate CD8+ responses, no patients have met the definition of response according to the above definition. Therefore, the study team is changing the definition of the primary endpoint to be the actual change from baseline for gp100(g209-2M) tetramer+ cells in the CD8+ T-cell population. The study will be stratified by cohort (NED/metastatic), but we expect the same immune response in each cohort.

For part 1 the 8-week primary immune outcome values CD8+ T-cell response will be compared between the two arms by using a Wilcoxon rank-sum test. Patients who discontinue from the study before week 8 will be assigned the lowest rank in this analysis. With one interim analysis, using an O'Brien-Fleming boundary to stop for efficacy, a one-sided significance level of 0.05, with 24 patients per arm, we will have 80% power to be able to detect an effect size of  $0.73^*SD(CD8+ T\text{-cell response})$ .

## Part 2

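### The consequences of a grade 3 toxicity are stated inconsistently, and removal for toxicity before week 8 would place patients at the lowest rank of the primary test, with R848-attributable removals only in Arm A

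*Combined protocol and SAP*

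**What the plan says.** Four passages deal with a grade 3 or greater toxicity.

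- Section 10.3, under the removal criteria, covers adverse events that make stopping treatment necessary. Its example is "any grade III or greater toxicity, attributable to the peptide vaccines or R848 (Resiquimod").
- Section 8.0, after the adverse event table: "any grade 3 or greater toxicity will result in a dose reduction of the application of R848 from twice a week to once a week".
- Section 6.0, for gel on tumors in Part 2: "with the option of dose reducing from twice to once a week should patients experience any grade 3 or greater toxicity".
- Section 8.0, opening paragraph: "patients who experience any Grade III or greater autoimmune reactivity, except for local skin reactions, will be taken off the study".

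Two sentences in Section 8.0 halt accrual. The first: "The occurrence of 3 patients with Grade III or greater toxicity will stop the entry of the study". The second follows the frequency-reduction rule: "if this is required in 3 patients, we will temporarily halt accrual".

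On the Part 1 schedule, the Section 11.0 Overview says patients randomised to gel "will have the gel applied to the gp100(g209-2M) vaccine site weekly", and Section 3.4 agrees. Section 2.6, however, plans application twice a week in the study, with once a week as the fallback.

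For the primary analysis, Section 11.0 (Part 1) states: "Patients who discontinue from the study before week 8 will be assigned the lowest rank in this analysis". Section 10.1 lets patients who recur or progress before week 16 complete their laboratory evaluations. No section says the same for patients removed for an adverse event.

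**The concern.** The same attributable grade 3 event can mean removal, a required reduction, an optional reduction, or no removal, depending on which section is followed. Two investigators could each follow the protocol and manage the same event differently.

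The analysis has a related problem. The primary objective is T-cell priming, measured by the week-8 CD8+ tetramer response. If removal for toxicity before week 8 counts as discontinuing from the study, the patient is ranked worst on an immune outcome because of a tolerability event. Among randomised patients only Arm A receives R848 before week 8, so removals attributed to R848 can occur only in that arm. In a trial of 24 per arm, a few such patients could hide a real effect.

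**Working it through.** **1. Which rules can operate when.**

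| | Part 1 (weekly gel, Arm A only) | Part 2 (gel on tumors twice a week) |
|---|---|---|
| Section 10.3, removal | Applies, either arm | Applies |
| Section 8.0, reduction | Cannot be carried out on a weekly schedule; Arm B has no gel | Applies, required |
| Section 6.0, reduction | Not written for Part 1 | Applies, optional |
| Section 8.0, autoimmune removal | Applies, local skin reactions excepted | Applies, local skin reactions excepted |

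Removal against reduction is therefore mainly a Part 2 conflict. In Part 1 the conflict is Section 10.3 (any attributable grade 3 or greater) against the opening of Section 8.0 (autoimmune only). The schedule in Section 2.6 also has to be reconciled with Sections 3.4 and 11.0.

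**2. Accrual halt.** One trigger counts patients with grade 3 or greater toxicity. The other counts patients who need the frequency reduction. On a weekly Part 1 schedule no Part 1 event can enter the second count.

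**3. The plan's own power.** Inputs from Section 11.0: 24 per arm, effect 0.73 SD, one-sided 0.05, nominal levels 0.0056 (interim) and 0.0482 (final).

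- Normal formula: Φ(0.73 × √(24/2) − 1.645) = Φ(2.529 − 1.645) = Φ(0.884) = 81.2%.
- Noncentral t: 80.1%.
- Two-look normal design with Wilcoxon efficiency 3/π: 79.3%.
- O'Brien-Fleming-type alpha spending at half information gives 0.00557 and 0.0482, overall alpha 0.0500.

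The stated 80% and both nominal levels reproduce.

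**4. Effect of the lowest-rank rule.** The method was simulation of the two-look, tie-corrected Wilcoxon test: normal outcomes, interim at 12 per arm, 60,000 runs per scenario, randomly chosen patients set to a tied lowest value. The removal counts are assumptions.

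| Lowest-ranked, Arm A / Arm B | Power at 0.73 SD | One-sided type I error |
|---|---|---|
| 0 / 0 | 77.9% | 5.2% |
| 1 / 0 | 66.5% | 2.6% |
| 2 / 0 | 51.1% | 1.1% |
| 3 / 0 | 35.0% | 0.4% |
| 3 / 1 | 41.7% | 0.7% |
| 3 / 3 | 58.2% | 2.2% |

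The first three removals in Arm A alone cost about 11, 15 and 16 points in turn.

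**5. Hand check.** With no removals, P(A > B) = Φ(0.73/√2) = 0.697. With k Arm A patients ranked lowest it becomes 0.697 × (24 − k)/24. The null standard error is √(49/(12 × 24 × 24)) = 0.0842, and the final critical value for 0.0482 is 1.663.

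- k = 0: (0.697 − 0.5)/0.0842 = 2.34; Φ(2.34 − 1.663) ≈ 75%.
- k = 3: 0.697 × 21/24 = 0.610; (0.610 − 0.5)/0.0842 = 1.31; Φ(1.31 − 1.663) ≈ 36%.

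This ignores the interim look and uses the null variance, and it agrees with the simulation to within about three points.

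**The case against.** Several points on the other side stand.

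- **Route to the primary test.** A reader might infer that removal against reduction is what damages the primary comparison. The documents do not support that. The reduction is workable mainly in Part 2, when the before-week-8 rank rule can no longer apply. The link runs through Section 10.3 together with Section 11.0.
- **Force of Section 10.3.** Grade 3 toxicity is given as an example, within text about events that make stopping treatment necessary and usually threaten life or functioning. That leaves room for judgement, though the example names the same event that Section 8.0 handles by reduction.
- **Accrual halt.** A reader might call the two triggers contradictory. The second is introduced as an addition, so both can stand, and the first already covers Part 1 events. What is missing is a statement of how they relate.
- **Both arms are exposed.** Section 10.3 also covers peptide-vaccine toxicity, and the rank rule applies to either arm for any reason. The zero-in-Arm-B rows are the unfavourable end of the range. Three patients with grade 3 or greater toxicity would also trigger the first accrual halt and a reassessment.
- **The rank rule is prespecified and conservative.** Scoring discontinuation as the worst outcome is a legitimate choice in some settings. It fits poorly here because the objective is immune priming, not tolerability.
- **Missing samples.** Using observed values helps only if a week-8 sample is taken, and sampling after adverse-event removal is not currently provided for.

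**Conclusion.** The inconsistency is real and lies in current operative text: Sections 6.0, 8.0 and 10.3 attach different consequences to the same event, and Section 2.6 disagrees with Sections 3.4 and 11.0 on gel frequency. No view is taken here on which clinical rule is right.

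Separately, Section 10.3 combined with the lowest-rank rule biases the primary comparison against R848 to the extent that R848 toxicity leads to removal before week 8. Under the assumed counts, power falls from about 78% to between 66% and 35% for one to three removals in Arm A alone; it is 42% with three against one and 58% with three in each arm. These figures assume normal outcomes, a true shift of 0.73 SD and removals unrelated to the immune response.

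Two stronger conclusions are not supported. The trial cannot be said to have 35% power, because the documents give no removal rate. Nor is there a raised risk of a false claim for R848: in every scenario with removals shown, type I error is below its no-removal value. If toxicity patients stay on study to week 8, the loss does not arise.

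**What to change.** 1. Reconcile Sections 2.6, 3.4, 6.0, 8.0, 10.3 and the Section 11.0 Overview, so that each part and arm has one stated gel schedule and one stated consequence of a grade 3 or greater toxicity. The choice of clinical rule belongs to the sponsor and investigators.
2. State in Section 8.0 how the two accrual-halt triggers relate, and which events in which part count towards each.
3. In Section 11.0, separate stopping treatment from leaving the study. Extend the Section 10.1 allowance so that patients who stop for toxicity may, with consent, complete the blood draws already scheduled. Analyse any available week-8 value as observed, and assign the lowest rank only when no week-8 sample exists.

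The cost is a wording amendment, a short change to the analysis section, and follow-up of a few patients for a draw already on the schedule. No additional patients are needed.
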